Study Design: This is a mixed methods feasibility study consisting of 3 parts and will investigate clinician and patient response to a ***simplified physical examination (SPE)*** used to inform post-concussion management. Part 1 (Experimental Study a.), a single-group pretest-posttest clinical design will provide preliminary (pilot) evidence of combined effect of assessment and treatment using the SPE to preselect those suited to manual treatment of the neck. Part 2 (Main Feasibility Study) a mixed methods study will consist of a nested qualitative study examining service providers attitudes toward use of the SPE to identify individuals appropriate for neck rehabilitation following concussion (Orthopedic Manual Treatment (OMT) and neuromuscular/ sensorimotor retraining) and utility of this method in the context of current practice. Quantitative exploration of patient compliance, and satisfaction, as well as any adverse reactions to treatment will also contribute to determining overall feasibility of using the SPE. Part 3 (Experimental Study b.), a 3-month follow up will assess long-term effect of treatment selection based on use of the SPE. Combined evidence from these studies will be used to inform development of a future protocol for a pilot randomised, non-inferiority, controlled trial.

Study Procedure and Setting: Participants will take part in one screening session in the Laboratories located at the School of Physiotherapy, University of Otago, Dunedin (referred to as “*screening session*”). Participants identified as eligible to enter the treatment arm of the study will then be invited to participate in further treatment session (referred to as “*treating sessions*”) where they will attend 2 physiotherapy sessions per week for 4 weeks at physiotherapy clinics local to Dunedin. Follow-up assessment (referred to as “*follow up sessions*”) for participants entering the treatment arm of the study will then be conducted 1 week and 3 months following cessation of treatment and will take place at the University of

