Smooth Pursuit/ Neck Torsion: The patient is seated comfortably with the head positioned in neutral and is asked to follow a slow-moving target approximately 40° (20° to the right and to the left). The patient is instructed to keep the head still while observing the target. This is repeated in neutral and in cervical torsion (rotation of the trunk to the left or right underneath the head, rather than turning the head left or right). Differences in eye motion are noted with differences between neutral and cervical torsion being associated with cervical sensorimotor disturbance, as opposed to vestibulo-ocular impairment which may be more apparent in neutral [54].

Ethical considerations for clinical measures of neck function and head movement control: There is a risk of symptomatic aggravation such as increased dizziness or nausea, or soreness in the neck muscles following assessment based on previous participant reports, however all symptoms have been short-lived and (dizziness usually settles with a short break following test performance). Muscle endurance tests have the potential risk of mild muscle strain or post exercise soreness. However, there is minimal likelihood of injury as testing is performed within the participants tolerance levels. Any muscle discomfort or soreness associated with the endurance test is usually short lived and resolves within 24-48 hours. Participants will also

be offered a short break if required during testing to allow time for symptoms to settle.

Measures of vestibulo-ocular performance: will be used to identify individuals with evidence of vestibulo-ocular impairment [55]. Vestibulo-ocular assessment will commence with oculomotor screen of eye movement to determine presence or absence of baseline oculomotor paresis or palsy [56] which may unduly influence VOS results. This will be followed by completion of the oculomotor and vestibular testing suite (recorded as present/ absent: nystagmus, saccades, strabismus, canalith disorders, vestibulo-ocular reflex function impairment [gain]) on the ICS Chartr 200 VNG System (Otometrics; Taastrup; Denmark). Two or more positive tests will identify individuals with evidence of vestibulo-ocular impairment [57, 58].

Description of the vestibulo-ocular assessment is as follows:

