impairment appropriate referral should be made. It is important to remember that performance of the VOMS requires a substantial amount of head on neck motion, therefore consideration should be given to the cervical spine as a potential source of increase in symptom reporting. This is especially the case where cervical sensorimotor assessment appeared to indicate the presence of dysfunction.

Ethical considerations for vestibular dysfunction measures: There is a risk of symptomatic aggravation such as increased dizziness or nausea following assessment based on previous participant reports, and the potential to identify the presence of BPPV, oculomotor and vestibular disorders of a central origin unrelated to concussion. However, all reported symptoms have been short-lived and (generally dizziness has settled with a short break following test performance). Permission will also be sought from participants to share information related to findings of the assessment with their physician. Participants will also be offered a short break if required during testing to allow time for symptoms to settle.

Order of testing will be performed to minimise symptom exacerbation and influence of preceding outcomes on those to follow and therefore will not be randomised and will be performed consistently in the same order.

Following completion of the screening session participants identified as eligible for entry to the treatment arm of the study will be provided with activity monitors (ActiGraph activity monitors [GT3x, GT9x]).

Physical Activity Levels and Sleep: Participants will be asked to wear ActiGraph activity monitors (GT3x, GT9x) on their waist/ hip and wrist to measure physical activity during the first 7 days following the screening session. Both ActiGraph activity monitors are tri-axial and solid state accelerometers [64, 65], and have been validated for use in adult populations [66, 67]. Participants will be asked to complete a day time activity log (including time when monitors are removed for personal care activities, when vigorous activity was performed etc.) for interpretation of data collected by the activity monitors, and a sleep log to evaluate sleep quality of the previous night's sleep [68, 69]. The sleep log will be manually completed in the morning in relation to the previous night's sleep.

Eligibility for Entry to Treatment Arm:

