We will use Thematic Analysis, an evaluative deductive approach to analyse the qualitative focus group and interview data, as described by Clarke and Braun [77]. The SC will code each transcription and one of the researchers will code every third transcription, grouping the codes into themes and sub-themes. An iterative process will be used within the research team to define the main themes and emerging models related to the study aims. In this way thematic analysis will be reflexive to aid in identification of any instances where the PI's beliefs may unduly influence identification of these main themes.

Quantified feasibility outcomes: activity, compliance, and adverse event monitoring

Participants will record daily performance of home exercises prescribed by the treating therapist in an activity-log (yes/ no, minutes of exercise per day) to determine treatment compliance. Non-attendance at scheduled treatment sessions will be recorded by the treating therapist (yes/no per session) as well as any adverse reactions to treatment (number). Participants will complete an exiting questionnaire to assess patient satisfaction [78].

Experimental Outcomes:

Experimental outcome measures (experimental studies a. & b.) will include but are not limited to:

Category	Exploratory OM
Cervical Spine	

Kinematic Assessment - Virtual Reality	Total range of motion (deg) Peak Velocity – Rotation R (deg/s) Peak Velocity – Rotation L (deg/s) Peak Velocity – Rotation Ext. (deg/s) Global head motion accuracy (deg)
Muscle Function (CFET)	Total time (sec)
Manual Spinal Examination	Pos/ neg
Sensorimotor Function (JPE)	Degrees Error (deg) Neck Disability Index (tot/ 50) Headache Impact Test-6
Vestibulo-Ocular	
VNG OM Assessment	Full Assessment (≥ 2 pos/neg overall (pos/neg) ; pos/neg per assessment)
VOMS assessment	Increase in symptoms (11- point NRS) ; avg NPC > 5cm Dizziness Handicap Index
Participant Outcomes	
Physical Activity : Actigraphy	Minutes of Vigorous Physical Activity, min/day Physical Activity (TAC/d; steps/d; PAEE - kcal/kg/day) Activity log Consensus Sleep Diary PROMIS sleep questionnaires IPAQ (METs) Fatigue Severity Scale
Quality of Life	EuroQol-5D-5L (EQ VAS)

Data Management

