Clinical data will be entered directly into the study's online data recording form which only the PI, SC and members of the research team will be able to access. Data in this form will be stored under a unique identifier generated during the initial screening session with the SC. Where raw data requires further analysis, it will be deidentified (VR and VNG outcomes) and routinely uploaded to the PIs (OG) password protected laptop or the password protected study laptop. Data collected using VR and VNG will be collected on the devices using the participants unique identifier.

Statistical Analysis

Descriptive analyses will be performed on sociodemographic data. Exploration of central tendency of all data will be evaluated using Kolmogorov-Smirnov and Shapiro-Wilk tests. Where data is significantly skewed, attempts will be made to transform using suggested methods [57]. Individual demographic variables (sex, age, BMI, IPAQ score) which could reasonably be expected to influence quantitative outcomes will be analysed for significance using univariate linear regression and included in models.

Objective 1:

Quantified feasibility outcomes: activity, compliance, and adverse event monitoring

- a. Descriptive statistics will be used for recruitment frequency and the number of eligible participants, the drop-out rate, and degree of missing data for the patient rated and clinical outcomes measures. The programme will be considered feasible if 80% of patients complete the programme until formal discharge based on the physiotherapists' assessment and treatment documentation.
- b. Adherence to the intervention by auditing and summarising patients' logbooks and the physiotherapists' assessment and treatment documentation. The SC will audit the documentation. Adherence will be considered acceptable if 80% of exercises had been recorded in the patient's logbooks.
- c. Adverse events from the treatment will be determined by auditing the physiotherapists' assessment and treatment documentation as well as inclusion of formal reports submitted to the study or HEC in the event of serious adverse events. Number of events will be considered.
- d. Patient satisfaction score (/12) from the patient satisfaction exiting questionnaire will be calculated and mean and 95% CI will be reported.

Triangulation of qualitative (analysis described above) and quantitative outcomes [79] will determine overall feasibility of using the SPE to inform treatment management.

Objective 2:

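### The adverse-event count in Objective 1, item c, covers treatment reactions only, so non-serious SPE reactions and those treatment reactions first reported after the last session fall outside a count that feeds the SPE feasibility judgement

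*Protocol*

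**What the plan says.** Item c (Protocol, Statistical Analysis, Objective 1) fixes both what is counted and where it is found. The object is set by its opening words, "Adverse events from the treatment will be determined by auditing the", which lead on to the records kept by the treating therapists. The two sources are given as "assessment and treatment documentation as well as inclusion of formal reports submitted to the study or HEC in the event of serious adverse events". The result is a number of events with no threshold.

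The outcome section (Quantified feasibility outcomes) agrees. The treating therapist records missed sessions "as well as any adverse reactions to treatment (number)".

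The use of the count is also stated. Under Study Design, "any adverse reactions to treatment will also contribute to determining overall feasibility of using the SPE". At the end of Objective 1, triangulation of the qualitative and quantitative outcomes "will determine overall feasibility of using the SPE to inform treatment management".

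The protocol expects the examination itself to cause some reactions. For the neck tests: "There is a risk of symptomatic aggravation such as increased dizziness or nausea, or soreness in the neck muscles following assessment", and "Any muscle discomfort or soreness associated with the endurance test is usually short lived and resolves within 24-48 hours". For the vestibular tests: "There is a risk of symptomatic aggravation such as increased dizziness or nausea following assessment based on previous participant reports". Both sections describe these symptoms as short-lived.

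**The concern.** Objective 1 is the feasibility of implementing the SPE in primary care, and feasibility is the primary outcome. How well patients tolerate the examination bears on that. The Background lists symptom worsening for days afterwards among the drawbacks of broad assessment after concussion. Yet the one adverse-event measure that feeds the judgement is confined to the treatment that follows the SPE.

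The sources cannot make up the difference. The SPE is done in the university laboratory by the principal investigator or the study coordinator (the protocol names each in different places), not by the treating physiotherapist. It is repeated at both follow-up visits, after treatment has ended. Non-serious reports that reach the study by other routes are not named as a source.

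At stake is a descriptive result: the trial would not be able to report a count of adverse events for the examination it is testing.

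**Working it through.** **Inputs**
- 160 screened, 60 eligible, 50% decline, 10% drop out (Study power).
- Treatment twice weekly for 4 weeks, starting at most 2 weeks after screening (Treatment sessions procedure).
- SPE repeated 1 week and 3 months after treatment ends (Follow up sessions).

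**The plan's own figures**
- Starting treatment: 60 x (1 - 0.5) = 30.
- Complete at all time points: 30 x (1 - 0.1) = 27.

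Both agree with Study power.

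**Scope of item c**
- Planned treatment sessions: 30 x 2 x 4 = 240. Reactions to these are in scope.
- Planned SPE sessions: 160 + 2 x 27 = 214, or 160 + 2 x 30 = 220 without drop-out, which is the basis comparable with 240. For non-serious reactions, none is in scope.
- Examined but never treated: 160 - 30 = 130, and 130/160 = 81%. These people have no treating-physiotherapist record. For the other 30 a record exists, but the restriction to events from the treatment still leaves SPE reactions out.

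**Which events are in the count as written**

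| Event | Counted under item c? |
|---|---|
| Treatment reaction noted at a session, or arising between sessions and noted at the next | Yes |
| Serious treatment event, at any time, formally reported | Yes |
| Non-serious treatment reaction first reported after the last session | No named source |
| Non-serious SPE reaction, at screening or follow-up | Outside the stated scope, and no named source |

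**Other routes in the protocol**
- Adverse event management sends any adverse event at once to the internal Health & Safety Committee. Potential problems invites participants to contact the principal investigator if symptoms do not subside or they fear that pain may return. Item c draws on formal reports only for serious events, so non-serious reports made this way do not enter the count.
- Soreness that clears within 24-48 hours would usually not prompt such a contact, so it could not be recovered at analysis.
- The 1-week visit falls about 4 + 1 = 5 to 2 + 4 + 1 = 7 weeks after screening, and the 130 untreated people have no such visit.

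**What a count could support.** If SPE events were counted at screening and none occurred in 160 people, the exact two-sided 95% upper limit would be 1 - 0.025^(1/160) = 0.0228, or 2.3%. This illustrates precision only. It presupposes a definition that leaves out symptoms provoked on purpose by the tests.

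**The case against.** The strongest reply is that nothing here contradicts itself. Study Design, the outcome section and item c all define the measure as reactions to treatment, and the hypothesis concerns clinician attitude to the SPE together with compliance and satisfaction with the treatment. On that view the construct is whether people selected by the SPE tolerate and complete treatment. The consistency is real, and no internal contradiction is claimed. But the objective and the triangulation name feasibility of using the SPE, and reactions to the SPE itself are left out by a stated rule rather than by an omitted detail.

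Other points on that side stand in full:
- A reader might infer that harms of the SPE go unmanaged. They do not: any adverse event, serious or not, has a reporting route.
- A reader might infer that symptom provocation by the SPE is unmeasured. The Vestibular Ocular Motor Screen (VOMS) records symptom increase on an 11-point scale, and the manual spinal examination requires a pain rating. These are test results, not adverse events, and they cover only parts of the examination.
- A reader might infer that late treatment reactions in general are lost. Only non-serious ones first reported after the last session are. Worsening could still show in the follow-up questionnaires, though not as counted events.
- Simply recording reactions at the end of each SPE would mix harm with positive tests, since the VOMS is read by symptom reproduction and a positive manual examination needs provoked pain of at least 3/10. An end-of-session record also misses soreness that begins later.

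The practitioner focus groups may raise challenges with the SPE, but they give opinions, do not include patients and yield no count.

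**Conclusion.** The point holds as a limit on scope and sources. Item c leaves out non-serious reactions to all 214 planned SPE sessions and non-serious treatment reactions first reported after the last session, while the count contributes to judging SPE feasibility.

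The 214 and the 130 of 160 (81%) rest on the planned recruitment figures. They say what is out of scope, not how many events would be missed; no reaction rate is given.

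A reader might go further and conclude that the feasibility decision is wrong or that participants are at risk. The protocol supports neither. Item c has no threshold, expected reactions are described as short-lived, safety reporting is in place, and spontaneous reports could still be added at analysis. The change is worth making because it is cheap, but the study does not depend on it.

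**What to change.** Reword item c along these lines:

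> Adverse events from the SPE and from the treatment will be determined from the treating physiotherapists' documentation; events noted by the PI or SC at each SPE session; one standard question at the 1-week and 3-month visits; participant contacts with the PI; and all adverse-event reports made under Adverse event management, serious or not. An SPE reaction is a symptom that stops the examination, does not settle with a short break, or persists after the session. Symptom increase on the VOMS and pain provoked by the manual examination are test results and are not counted as such.

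Report SPE events (denominator: all screened, with follow-up SPEs shown separately) apart from treatment events (denominator: all who started treatment), descriptively.

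**Cost.** No new visits. At an assumed 1 minute per record, 214 session records plus one question at 2 x 27 = 54 follow-up visits is 268 minutes, about 4.5 staff hours over the study.

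**Limits.** There is slightly more recording, and without a comparator some ordinary concussion symptoms will be counted as reactions. Short-lived soreness that begins after screening will still be under-counted unless a brief message is sent 1 to 3 days later. That is not in the 4.5 hours: at the same assumed minute, 160 messages would add 160 minutes, about 2.7 hours.

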1. To examine feasibility of implementing a simplified physical examination (SPE) aimed at identifying patients suited to cervical spine OMT and neuromuscular/ sensorimotor retraining, within a New Zealand Primary Health Care setting.
2. Based on response to treatment over time, to provide preliminary evidence regarding the

efficacy of the simplified physical examination to accurately identify individuals who may be suited to physiotherapeutic intervention consisting of OMT and neuromuscular/sensorimotor retraining. Included in this objective will be use of data to validate a clinical objective oculomotor screen to improve clinical utility of the SPE.

We hypothesise that using the SPE will aid in identification of individuals suited to orthopedic manual therapy of the neck. Consequently, primary outcomes including clinician attitude toward using the SPE in a primary health care setting, and participant compliance and satisfaction with the OMT intervention will be positive. Further we anticipate that measurable improvement (objectively assessed neck function and clinical presentation) in response to the selection to neck OMT based on the SPE will be observable over time. Results will therefore support feasibility of using the SPE for acute patient assessment, as well as the clinical efficacy of this approach for managing neck related signs and symptoms following concussion.

Methods

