Today's date	4/5/11								
1. What time did you get into bed?	10:15 p.m.								
2. What time did you try to go to sleep?	11:30 p.m.								
3. How long did it take you to fall asleep?	55 min.								
4. How many times did you wake up, not counting your final awakening?	3 times								
5. In total, how long did these awakenings last?	1 hour 10 min.								
6. What time was your final awakening?	6:35 a.m.								
7. What time did you get out of bed for the day?	7:20 a.m.								
8. How would you rate the quality of your sleep?	 Very poor  Poor  Fair  Good  Very good	 Very poor  Poor  Fair  Good  Very good	 Very poor  Poor  Fair  Good  Very good	 Very poor  Poor  Fair  Good  Very good	 Very poor  Poor  Fair  Good  Very good	 Very poor  Poor  Fair  Good  Very good	 Very poor  Poor  Fair  Good  Very good	 Very poor  Poor  Fair  Good  Very good	
9. Comments (if applicable)	I have a cold								

(xi) *Participant Satisfaction Questionnaire*

1. Please rate how satisfied you were with the physiotherapy treatment you received.

1	2	3
Not satisfied	Satisfied	Very much satisfied

2. Please rate how satisfied with the frequency of the physiotherapy treatments.

1	2	3
Not enough	Just right	Too much

3. Please rate how satisfied you were with the duration of the treatments.

1	2	3
Too short	Long enough	Too long

4. Please rate how satisfied you were with the time spent with the physiotherapist during the treatments.

1	2	3
Not enough	Just right	Too much

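### The satisfaction score out of 12 counts 'too much' treatment as the best answer on three of its four items, so it does not rise with satisfaction

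*Protocol*

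**What the plan says.** Under Statistical Analysis, Objective 1, item d, the Protocol states: "Patient satisfaction score (/12) from the patient satisfaction exiting questionnaire will be calculated and mean and 95% CI will be reported". The form is printed in full in Appendix 1 (xi). Item 1 reads "Please rate how satisfied you were with the physiotherapy treatment you received" and its codes run from 1 (not satisfied) to 3 (very much satisfied). The other three items ask about amount:

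- Item 2: "Please rate how satisfied with the frequency of the physiotherapy treatments"
- Item 3: "Please rate how satisfied you were with the duration of the treatments"
- Item 4: "Please rate how satisfied you were with the time spent with the physiotherapist during the treatments"

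On items 2 to 4, code 1 means too little, code 2 about right and code 3 too much or too long. The Protocol gives no scoring instruction or recoding for this form.

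Satisfaction is listed under Primary Outcomes: Feasibility. The hypothesis in Study Objectives is that "participant compliance and satisfaction with the OMT intervention will be positive". The quantitative feasibility results are then triangulated with the qualitative findings, and this "will determine overall feasibility of using the SPE to inform treatment management".

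**The concern.** A total is useful as a satisfaction score only if a more favourable answer on any item raises it. Here that is true of item 1 alone. On items 2 to 4, each move from the favourable middle answer to a complaint of excess adds a point, and each move to a complaint of too little removes one. Three quarters of the score therefore measures perceived amount of treatment, with more counted as better.

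A reader who sees a mean out of 12 will take values near 12 as good and values around 9 as middling. In fact 9 is what a cohort with no complaints at all would produce, and a mean above 9 requires some patients to report excess. The planned programme is two sessions a week for four weeks, so answers of that kind are plausible. The figure would enter the overall feasibility conclusion, which is meant to inform a later randomised trial.

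**Working it through.** **Inputs** (Protocol, Appendix 1 (xi), printed codes)

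| Item | Code 1 | Code 2 | Code 3 | Best code |
|---|---|---|---|---|
| 1 Overall | not satisfied | satisfied | very much satisfied | 3 |
| 2 Frequency | not enough | just right | too much | 2 |
| 3 Duration | too short | long enough | too long | 2 |
| 4 Time with therapist | not enough | just right | too much | 2 |

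**Step 1: reproduce the denominator.** Maximum of the plain sum = 4 items × 3 = 12, which matches the stated figure. The minimum is 4 × 1 = 4.

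**Step 2: score key patterns** (items 1, 2, 3, 4 in order)

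- Fully satisfied (3,2,2,2): 3 + 2 + 2 + 2 = 9
- Not satisfied, everything excessive (1,3,3,3): 1 + 3 + 3 + 3 = 10
- Very satisfied, one complaint of excess (3,3,2,2): 3 + 3 + 2 + 2 = 10
- Maximum (3,3,3,3): 12, the only pattern that reaches it
- Very satisfied, wanted more of everything (3,1,1,1): 6
- Not satisfied, amounts right (1,2,2,2): 7

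**Step 3: count all patterns.** There are 3⁴ = 81. Totals of 4, 5, …, 12 occur 1, 4, 10, 16, 19, 16, 10, 4 and 1 times. Patterns above 9 number 10 + 4 + 1 = 15. By item 1 answer, one of these is *not satisfied*, four are *satisfied* and ten are *very much satisfied*. Without a code 3 on items 2 to 4 the total cannot exceed 3 + 6 = 9, so every one of the 15 contains at least one complaint of excess. Three further *not satisfied* patterns tie with the ideal at 9: (1,2,3,3), (1,3,2,3) and (1,3,3,2).

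**Step 4: group means.** The Protocol expects 27 participants with complete data. If all 27 were fully satisfied, the mean would be 9.0. If all were (1,3,3,3), it would be 10.0. With 14 of (1,3,3,3) and 13 fully satisfied, it would be (14 × 10 + 13 × 9)/27 = 257/27 = 9.52, higher than for the cohort with no complaints.

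**Step 5: effect of recoding items 2 to 4.** Score the middle answer 3 and either extreme 1. The fully satisfied patient then scores 3 + 9 = 12, the only pattern at the maximum, and (1,3,3,3) scores 1 + 3 = 4. If the extremes score 2 instead, the two scores are 12 and 1 + 6 = 7. Either version keeps the denominator of 12 and restores the direction.

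Recoding does not cure everything. (3,1,1,1) becomes 6 (or 9 with extremes at 2), still below (1,2,2,2) at 1 + 9 = 10, because three items about amount outweigh the one about satisfaction.

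**The case against.** The Protocol never says the codes are summed. A denominator of 12 fits a recoded score as well as a raw one, and the rule might sit in the cited source of the questionnaire or in a statistical analysis plan that is not at hand. That is fair as far as it goes: summing is an inference. But the printed codes are the only scoring the document gives. The same appendix prints reversed codes on the positively worded PROMIS sleep items and gives scoring instructions for the NDI, DHI and HIT-6, so where scoring needs explaining it is explained. Nor would an unstated recode be harmless, since the two simple versions above put the same patient at 4 or at 7.

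It can also be said that the harm is limited. No pass mark is attached to the score; the only numerical feasibility thresholds are the 80% rules for programme completion and recorded exercises. The score is one descriptive strand in an uncontrolled study. A *not satisfied* patient strictly outscores the ideal in only one pattern. The count of 15 in 81 is not a probability, and most of those patterns belong to patients who are satisfied overall. The answers can be rescored later if they are kept item by item. All of this stands and bears on how serious the consequence is. It does not make the total a measure of satisfaction.

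**Conclusion.** The concern holds. On the only scoring the Protocol supports, the score is not ordered by satisfaction: a cohort with no complaints averages 9 out of 12, and each complaint of excess pushes the mean up. The mean and 95% CI therefore cannot show whether the hypothesis of positive satisfaction is met, and they can move in the wrong direction. The conclusion assumes that the score is the plain sum of the printed codes. That assumption would fail only if a recoding were laid down somewhere other than this Protocol. No formal decision rule is affected, but a named primary feasibility outcome is.

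**What to change.** Replace the total in Objective 1, item d. Report item 1 as the satisfaction outcome, with the number and percentage in each category and a 95% CI. Report items 2 to 4 as three-category distributions, with the percentage choosing the middle answer as the favourable result and the two extremes shown separately, since wanting less and wanting more have different implications for the next trial.

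If a single score is still wanted, state the recoding in the Protocol: middle answer highest on items 2 to 4, and a specified value for the extremes. Present it alongside item 1, because the three items about amount would still dominate it.

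The cost is one reworded analysis line, with no new data, patients or visits, provided the four answers are stored individually. It is best settled before any satisfaction data are examined.
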